2.4.5.1 Analyses of adverse events

Generalities

The primary focus of adverse event reporting will be on the on-treatment period. Pre-treatment and post-treatment adverse events will be described separately.

If an adverse event date/time of onset (occurrence, worsening, or becoming serious) is incomplete, an imputation algorithm will be used to classify the adverse event as pre-treatment, on-treatment, or post-treatment. The algorithm for imputing date/time of onset will be conservative and will classify an adverse event as treatment emergent unless there is definitive information to determine it is pre-treatment or post-treatment. Details on classification of adverse events with missing or partial onset dates are provided in Section [2.5.3](#).

Adverse event incidence tables will be presented by SOC and PT, sorted in alphabetical order for each treatment group, the number (n) and percentage (%) of patients experiencing an adverse event. Multiple occurrences of the same event in the same patient will be counted only once in the tables within a treatment phase. The denominator for computation of percentages is the safety population within each treatment group.

Sorting within tables ensures the same presentation for the set of all adverse events within the observation period (pre-treatment, on-treatment, and post-treatment). For that purpose, the table of all treatment-emergent adverse events presented by SOC and PT sorted by the internationally agreed SOC order and decreasing frequency of PTs within SOCs will define the presentation order for all other tables unless otherwise specified. Sorting will be based on results for the experimental arm given with the highest dose.

Analysis of all TEAEs

The following TEAE summaries will be generated for the safety population.

- Overview of TEAEs, summarizing number (%) of patients with any
 - Treatment-emergent adverse event
 - Serious treatment-emergent adverse event
 - Treatment-emergent adverse event leading to death
 - Treatment-emergent adverse event leading to permanent treatment discontinuation (defined when FQ is taken, not OZ439)
- All TEAEs by primary SOC and PT, showing number (%) of patients with at least 1 treatment-emergent adverse event sorted by the SOC internationally agreed order. The other levels (PT) will be presented in alphabetical order
- All TEAEs by primary SOC and PT, showing the number (%) of patients with at least 1 treatment-emergent adverse event, sorted by the internationally agreed SOC order and by decreasing incidence of PTs within each SOC. This sorting order will be applied to all other tables, unless otherwise specified
- All treatment-emergent adverse events regardless of relationship and related to FQ, related to OZ439, by primary SOC and PT, showing the number (%) of patients with at least 1 treatment-emergent adverse event, sorted by the internationally agreed SOC order. The other levels (PT) will be presented in alphabetical order

- All treatment-emergent adverse events by maximal severity, presented by primary SOC and PT, showing the number (%) of patients with at least 1 treatment-emergent adverse event by severity (ie, mild, moderate, or severe), sorted by the sorting order defined above

Analysis of all treatment emergent SAEs

- All treatment-emergent SAEs by primary SOC and PT, showing the number (%) of patients with at least 1 serious treatment-emergent adverse event, sorted by the internationally agreed SOC order. The other levels (PT) will be presented in alphabetical order
- All treatment-emergent SAEs regardless of relationship, related to FQ, related to OZ439, by primary SOC and PT, showing the number (%) of patients with at least 1 treatment-emergent serious adverse event, sorted by the internationally agreed SOC order. The other levels (PT) will be presented in alphabetical order

Analysis of all TEAEs leading to permanent treatment discontinuation

All treatment-emergent adverse events leading to permanent treatment discontinuation, by primary SOC and PT, showing the number (%) of patients sorted by the internationally agreed SOC order. The other levels (PT) will be presented in alphabetical order

Analysis of adverse events of special interest

All treatment emergent adverse events of special interest, by PT, showing the number (%) of patients, sorted by decreasing incidence of PT within each AESI category (without including the overall number of patients with at least 1 AESI).

In addition summaries of treatment emergent adverse events of the below categories:

- Hepatic disorders
- Torsade de pointes/QT prolongation

will be presented by primary SOC and PT, showing the number (%) of patients sorted by the internationally agreed SOC order. The other levels (PT) will be presented in alphabetical order.

Analysis of pre-treatment and post-treatment adverse events

If any pre-treatment or post-treatment adverse events lead to death or any pre-treatment adverse events lead to permanent treatment discontinuation, an overview of pre-treatment and/or post-treatment adverse events will be presented as a listing if only a few, otherwise as a summary (presenting number of patients with any pre-/post-treatment adverse events, serious pre-/post-treatment adverse events, pre-/post-treatment adverse events leading to death, pre-treatment adverse events leading to permanent treatment discontinuation) will be presented.

2.4.5.2 Deaths

Listing of deaths will be provided with flags indicating on-treatment, during follow-up or post-study status. Deaths in non-randomized patients or randomized but not treated patients will be listed separately.

2.4.5.3 Analyses of laboratory variables

For clinical chemistry and hematology parameters, measures expressed in local and standard international (SI) units are available. Only values expressed in SI units will be used for quantitative summary statistics.

The summary statistics (including number, mean, median, standard deviation, minimum and maximum) of all laboratory variables (values and changes from baseline) will be calculated for each visit or study assessment (baseline, each post-baseline time point, worst on-treatment value) by treatment group.

The incidence of PCSAs (list provided in Appendix A) at any time during the on-treatment period will be summarized by biological function and treatment group whatever the baseline level and/or according to the following baseline status categories:

- Normal/missing
- Abnormal according to PCSA criterion or criteria

Drug-induced liver injury

The liver function tests, namely AST, ALT, alkaline phosphatase, and total bilirubin, are used to assess possible drug-induced liver toxicity. The proportion of patients with PCSA values at any post-baseline visit by baseline status will be displayed by treatment group for each parameter.

A graph of distribution (e-dish plot) of peak values of ALT versus peak values of total bilirubin will also be presented. The graph will be divided into 4 quadrants with a vertical line corresponding to 3 x ULN for ALT and a horizontal line corresponding to 2 x ULN for total bilirubin.

Listing of possible Hy's law cases identified by treatment group (eg, patients with any elevated ALT>3 x ULN, and associated with an increase in bilirubin ≥ 2 x ULN) with ALT, AST, alkaline

phosphatase, total bilirubin, and the following complementary parameters: conjugated bilirubin, creatine phosphokinase and serum creatinine.

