9.2 ADVERSE EVENTS

Adverse event of special interest

An AESI) is an AE (serious or nonserious) of scientific and medical concern specific to the Sponsor's product or program, for which ongoing monitoring and immediate notification by the Investigator to the Sponsor is required. Such events may require further investigation in order to characterize and understand them. Adverse events of special interest may be added, modified or removed during a study by protocol amendment.

- **Pregnancy** of a female subject entered in a study as well as pregnancy occurring in a female partner of a male subject entered in a study with IMP/NIMP;
 - Pregnancy occurring in a female patient entered in the clinical trial or in a female partner of a male patient entered in the clinical trial. It will be qualified as an SAE only if it fulfills one of the seriousness criteria (see Appendix 4).
 - Follow-up of the pregnancy in a female participant or in a female partner of a male participant is mandatory until the outcome has been determined (see Appendix 5)
- **Symptomatic overdose** (serious or nonserious) with IMP/noninvestigational medicinal product (NIMP)
 - An overdose (accidental or intentional) with the IMP/NIMP is an event suspected by the Investigator or spontaneously notified by the patient (not based on systematic pills count) and defined as at least twice the intended dose.

Of note, asymptomatic overdose has to be reported as a standard AE.

• Increase in alanine transaminase (ALT)): ALT ≥3 ULN (if baseline ALT <ULN) or, ALT ≥2 times the baseline value (if baseline ALT ≥ULN) will be reported as AESI.

Cases of ALT >3 ULN will be monitored according to the procedures indicated in Appendix 7.

Patients with abnormal ALT values at Day 28 will be followed up until ALT returns to normal values. A PK sample will be made at time of event for OZ439 and FQ (& SSR97213) concentration measurement.

An ALT increase ≥ 3 ULN is reportable as an SAE in any of the following situation:

- Possible Hy's law: ALT or AST >3x ULN and bilirubin >2x ULN (>35% direct bilirubin) in the absence of a serum alkaline phosphatase level >2x ULN. [If fractionation is unavailable, record presence of detectable urinary bilirubin on dipstick indicating direct bilirubin elevations and suggesting liver injury]) or
- when ALT $>10 \times ULN$,
- when associated with jaundice or,
- when associated with coagulation disorder (prothrombin time <50%) or,
- in presence of signs of hepatic encephalopathy.

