Low (adults)	≤ 25 g/L	
Creatine Kinase		
High, all grades	> 3 ULN	≥ 3 ULN
At least grade 1 (adults)	> 3 ULN	
At least grade 2 (adults)	> 10 ULN	
Sodium		
Low	≤ 129 mmol/L	≤129 mmol/L
High	≥ 160 mmol/L	≥150 mmol/L
Potassium		
Low	< 3 mmol/L	Birth/0 to 27 days old : ≤3.0 mmol/L 28 days/1 month to 16/18 years old : ≤3.5 mmol/L
High	≥ 5.5 mmol/L	Birth/0 to 27 days old : ≥7.0 mmol/L 28 days/1 month to 23 months old : ≥6.0 mmol/L 24 months/2 years to 16/18 years old : ≥5.5 mmol/L
Creatinine		
High	≥ 150 µmol/L	Birth/0 to <6 years old : >53 µmol/L 6 years to <12 years old: >90 µmol/L 12 years to 16/18 years old: >132 µmol/L
Increase from baseline		
At least grade 1 (adults)	≥ 30% change from baseline	
At least grade 2 (adults)	≥ 100% change from baseline	
Creatinine Clearance		

Laboratory parameter	Adults	Children
PCSA criteria n/N1 (%)		
Low, all grades	< 90 mL/min*	Birth/0 to 27 days old : < 25 mL/min/1.73m ² ** 28 days/1 month to 23 months old: < 45 mL/min/1.73m ² ** From 2 years old : < 60 mL/min/1.73m ² **
Mild (adults)	[60 – 90[mL/min*	
Moderate (adults)	[30 – 60[mL/min*	
Severe (adults)	[15 – 30[mL/min*	
End stage (adults)	< 15 mL/min*	
*MDRD or Cockcroft-Gault equation		
**GFR Bedside Schwartz Formula Based on normal ranges: 20 to 50 (<8 days), 25 to 80 (8 days to 1 month), 30 to 90 (1-6 months), 40 to 115 (6-12 months), 60 to 190 (12-23 months), 90 to 165 (2-12 years), 80-120 (After 12 years)		
BUN		
High	≥ 17 mmol/L	Birth/0 to 27 days old : ≥ 4.3 mmol/L 28 days/1 month to 16/18 years old: ≥ 6.4 mmol/L
Alanine Aminotransferase		
High, at least grade 1	> 3 ULN	≥ 3 ULN
High, at least grade 2	> 5 ULN	≥ 5 ULN
High, at least grade 3	> 10 ULN	≥ 10 ULN
High, at least grade 4	> 20 ULN	≥ 20 ULN
Aspartate Aminotransferase		
High, at least grade 1	> 3 ULN	≥ 3 ULN
High, at least grade 2	> 5 ULN	≥ 5 ULN
High, at least grade 3	> 10 ULN	≥ 10 ULN
High, at least grade 4	> 20 ULN	≥ 20 ULN
Alkaline phosphatase		
High	> 1.5 ULN	≥ 1.5 ULN
Total Bilirubin		
High, all grades	> 1.5 ULN	≥ 1.3 ULN
At least grade 1 (adults)	> 1.5 ULN	

Laboratory parameter	Adults	Children
PCSA criteria n/N1 (%)		
At least grade 2 (adults)	> 2 ULN	
Alanine Aminotransferase and tot bilirubin		
High	ALT > 3 ULN and TBILI > 2 ULN	ALT \geq 3 ULN and TBILI \geq 2 ULN
Direct bilirubin and total bilirubin		
High	BILDIR >35% TBILI and TBILI >1.5 ULN	BILDIR >35% TBILI and TBILI \geq 1.3 ULN

References:

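### The SAP's possible Hy's law listing selects on ALT only, whereas Protocol 9.2 defines such a case by ALT or AST

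*SAP*

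**What the plan says.** Protocol 9.2, in the section on adverse events of special interest, gives the only definition of possible Hy's law in the protocol: "ALT or AST >3x ULN and bilirubin >2x ULN (>35% direct bilirubin) in the absence of a serum alkaline phosphatase level >2x ULN". It is the first bullet under a sentence stating that an ALT increase of at least 3 x ULN "is reportable as an SAE in any of the following situation".

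SAP 2.4.5.3 plans a "Listing of possible Hy's law cases identified by treatment group". The parenthesis that follows opens with *eg* and gives the rule: "patients with any elevated ALT>3 x ULN, and associated with an increase in bilirubin" to at least 2 x ULN. AST, alkaline phosphatase, total and conjugated bilirubin, creatine phosphokinase and creatinine are displayed for the listed patients. They play no part in selecting them.

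Two other SAP outputs join a transaminase with bilirubin:

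- In SAP 2.4.5.3: "A graph of distribution (e-dish plot) of peak values of ALT versus peak values of total bilirubin will also be presented".
- In SAP Appendix B, the combined criterion for adults: "ALT > 3 ULN and TBILI > 2 ULN". The criterion for children uses the same two analytes with *at least* in place of *above*.

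The same SAP section also states: "The liver function tests, namely AST, ALT, alkaline phosphatase, and total bilirubin, are used to assess possible drug-induced liver toxicity".

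**The concern.** Protocol 3.3 names raised liver enzymes as an identified risk of both drugs, alone and in combination, and safety of the combination is a secondary objective. The Hy's law listing is the output a safety reader would consult first for a serious liver signal. Its label matches the term defined in Protocol 9.2, but its rule leaves out one of the two enzymes in that definition. SAP 1.6, which records the statistical changes made in the SAP, does not mention the difference, so it does not look deliberate.

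An empty listing could then be read as showing that no participant met the protocol's definition, when the listing had not tested for all of them.

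**Working it through.** No sample size, power or event figure bears on this point. The check compares the two rules term by term and then follows one constructed case through the planned outputs.

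**Step 1. The terms side by side (multiples of ULN).**

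| Term | Protocol 9.2 | SAP 2.4.5.3 listing | SAP relative to protocol |
|---|---|---|---|
| Transaminase | ALT or AST > 3 | ALT > 3 | narrower |
| Total bilirubin | > 2 | ≥ 2 | wider |
| Direct bilirubin | > 35% | no condition | wider |
| Alkaline phosphatase | not > 2 | no condition | wider |

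**Step 2. Which protocol-defined cases drop out.** Any case with bilirubin > 2 also has bilirubin ≥ 2, and the listing sets no direct-bilirubin or alkaline phosphatase condition. So a case that meets the protocol's terms fails the listing only if ALT ≤ 3, which means it qualified through AST > 3. The missing AST term is the only route of loss.

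**Step 3. A constructed case.** Take AST 4, ALT 2, total bilirubin 3 (50% direct) and alkaline phosphatase 1, all except the percentage in multiples of ULN.

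| Rule or output | Check | Result |
|---|---|---|
| Protocol 9.2 bullet | AST 4 > 3; bilirubin 3 > 2; 50% > 35%; ALP 1 not > 2 | met |
| SAP Hy's law listing | ALT 2 not > 3 | not listed |
| SAP e-DISH plot | ALT 2 lies below the 3 x ULN line | outside the Hy's law quadrant |
| Appendix B, ALT with bilirubin | ALT 2 not > 3 | not counted |
| Appendix B, AST alone | 4 > 3 | counted |
| Appendix B, bilirubin rows | total 3 > 1.5; direct 50% > 35% | counted |

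The participant is counted under AST and again under bilirubin. Those tables are by parameter and arm, so they do not show that both rises occurred in one person.

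**Step 4. Other routes to the case.** The laboratory trigger for the liver event of special interest in Protocol 9.2 uses ALT only. The MedDRA query in SAP Table 2 searches events already reported as adverse events. The listing of individual patients with abnormalities is specified in SAP 2.4.5.5, for ECGs; SAP 2.4.5.3 specifies no equivalent for laboratory data. An AST-driven case therefore surfaces as a case only if the investigator reports an event.

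**Step 5. The protocol's own wording.** The sentence above the bullet requires ALT ≥ 3. The cases lost in Step 2 have ALT ≤ 3. The two conditions overlap only at ALT exactly 3 x ULN. Read literally, the lead-in leaves the AST term almost nothing to do; read as a stand-alone definition, the bullet gives AST full weight. The text supports both readings.

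**The case against.** Several points on the other side are sound.

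- **The rule is introduced by *eg*.** It can be taken as an example rather than the complete criterion. That stands. But it is the only rule given, and a programmer would have nothing else to implement.
- **The protocol text is a reporting rule with an ALT lead-in.** Protocol Table 9 plans no Hy's law listing, and Step 5 shows that the source is itself inconsistent. This weakens any claim that the SAP breaches a clear protocol analysis. It does not remove the stated definition, and it means that both documents need attention.
- **AST can rise for reasons outside the liver.** The listing is a screen for review and already displays creatine phosphokinase and alkaline phosphatase, so a reader can judge an added case.

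Three stronger readings are tempting, and the documents do not support them.

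- **That the e-DISH plot and the combined Appendix B criterion are also faults.** Protocol Table 9 itself specifies peak ALT against peak total bilirubin. Protocol 10.3.2.4 leaves the abnormality criteria to the sponsor, and Appendix B cites the sponsor's standard version. Neither contradicts the protocol.
- **That AST-driven cases vanish from the report.** AST has its own four grades and its own counts, worst on-treatment values are summarized for all laboratory variables, and reported hepatic events are tabulated. What is lost is the joint identification of AST with bilirubin in one patient.
- **That the problem has a measurable size.** One patient among about 35 in an arm is 1/35 = 2.9%, but this is what any single patient contributes to any table. It says nothing about how often AST exceeds 3 x ULN with ALT at or below it and bilirubin raised.

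**Conclusion.** The mismatch is real and narrow. If the rule is programmed as written, the listing omits participants with AST above 3 x ULN, ALT at or below 3 x ULN and bilirubin raised to the protocol's level, and no other planned output joins AST with bilirubin. On every other term the listing is wider than the protocol, so nothing else is lost.

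The conclusion rests on two assumptions: that the *eg* rule is the one implemented, and that the Protocol 9.2 bullet is meant to give AST its own role despite its lead-in. If the lead-in governs, hardly any protocol-defined case is lost, but the two documents still describe possible Hy's law differently.

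Only descriptive safety output is affected; no test, estimate or power figure changes. The expected number of such cases is unknown, and may be zero. The change is still worth making, because liver enzyme elevation is an identified risk and the correction is simple.

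**What to change.** 1. In SAP 2.4.5.3, replace the example with a definite rule: ALT or AST above 3 x ULN, with total bilirubin of at least 2 x ULN.
2. Keep alkaline phosphatase and conjugated bilirubin as displayed columns, and flag the listed patients who also meet the direct-bilirubin and alkaline phosphatase conditions of Protocol 9.2. The listing then remains a wide screen, and the protocol-defined cases can be read from it.
3. Reconcile the ALT-only lead-in in Protocol 9.2 with the bullet that names ALT or AST, so that the reporting rule and the listing refer to a stated and consistent definition. Which reading is intended is for the sponsor to settle.
4. Optionally, add an AST version of the e-DISH plot or an AST-with-bilirubin row to Appendix B. Neither is needed for consistency with the protocol.

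Items 1 and 2 cost a line or two of SAP text and minor programming. AST, total bilirubin and alkaline phosphatase are already in the safety panel in Protocol Appendix 2, and direct bilirubin is called for there when total bilirubin is at or above ULN. Item 3 needs a protocol clarification. No new data are required.

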2.4.5.4 Analyses of vital sign variables

The summary statistics (including number, mean, median, standard deviation, minimum and maximum) of all vital signs variables (raw data and changes from baseline) will be calculated for each visit or study assessment (baseline, each post-baseline time point, worst on-treatment value) by treatment group.

The incidence of PCSAs at any time during the on-treatment period will be summarized by treatment group irrespective of the baseline level and/or according to the following baseline status categories:

- Normal/missing
- Abnormal according to PCSA criterion or criteria

2.4.5.5 Analyses of electrocardiogram variables

The summary statistics (including number, mean, median, standard deviation, minimum and maximum) of all ECG variables (central laboratory values and changes from baseline) will be calculated for each visit or study assessment (baseline, each post-baseline time point, and worst on-treatment value) based on the average of the triplicate assessments by treatment group.

The incidence of PCSAs at any time during the on-treatment period will be summarized by treatment group irrespective of the baseline level and/or according to the following baseline status categories:

- Normal/missing
- Abnormal according to PCSA criterion or criteria

Listings

Following listings will be produced, using all data, including rechecked or unplanned values, whatever the sources.

- A listing of individual data of subjects with any post-baseline PCSAs will be provided; raw data and absolute or percent change from baseline will be displayed depending on the parameter and values will be flagged when reaching the limits of the PCSA criteria;
- In addition, subjects with QTc/QTcB/QTcF >480 ms and/or change from baseline in QTc/QTcB/QTcF >60 ms will also be listed separately, using all post-dose time points.
- A listing of subjects with at least one abnormality in qualitative assessment (ie, abnormal 12-lead ECG) after the 1st dosing will be also provided.
- A listing of morphological abnormalities (ECG extracted from 12-lead ECG data).

2.4.5.6 *Physical Examination*

Physical Examination assessments will be listed.

2.4.5.7 *Analyses of other safety endpoints*

Not applicable.

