10.3.2 Safety analyses

All safety analyses will be performed on the Safety Population (see Table 7). The safety analyses are summarized in Table 9.

Table 9 - Safety analyses

Endpoint	Statistical Analysis Methods		
For secondary objectives	The summary of safety results will be presented by treatment arm thanks to descriptive statistics (summary tables, graphics). No formal inferential testing will be performed.		
• AEs	Frequency tables of TEAEs and SAEs by treatment arm during the on-treatment phase		
	Summary tables of participant count (%) for each AESI by treatment arm		
	Summary tables of deaths		
	incidence of liver-related AEs summarized by treatment arm		
 Clinical laboratory tests 	 Counts of participants with potentially clinically significant abnormalities (PCSAs) at any time during the on-treatment phase will be summarized by treatment arm in summary tables showing shifts from normal and abnormal baselines to postbaseline abnormalities. 		
• LFT	 raw data and changes from baseline summarized in descriptive statistics, by treatment arm and visit for all participants 		
	 time profile plots (mean+/- SD) on raw data and change from baseline 		
	 proportion of participants with PCSA values at any post baseline visit by baseline status will be displayed by treatment arm 		
	 graph of distribution (e-Dish plot) of peak values of ALT versus peak values of total bilirubin 		
	 normalization (to ≤1 x ULN or return to baseline) of elevated liver function tests summarized by categories of elevation 		
 Vital signs 	raw parameter value and change from baseline		
	 Counts of participants with post-baseline PCSAs in summary tables by treatment arm 		
• ECG	 Heart rate, PR-, QRS-, and QT-intervals, corrected QTc (Fridericia) will be analyzed as raw parameter value and change from baseline, as well as percent change from baseline for selected parameters 		
	 Counts of participants with post-baseline PCSAs in summary tables by treatment arm 		
	 A summary of ECG morphological assessments (for all high level types of comments by treatment arm 		
	 Summary plots (mean+/-SD) on raw data and changes from baseline, as well as percent change from baseline for selected parameters 		
Physical examination	 Summary tables of participant count (%) for each physical examination (general appearance, head and eyes, ears, nose and throat, chest and lungs, cardiovascular, 		

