At least grade 2	>220 ms and increase from baseline \geq 25%	
At least grade 3	>240 ms and increase from baseline \geq 25%	
QRS		
High, all grades	>110 ms	Birth/0 to 27 days old : \geq 85 ms 28 days/1 month to 23 months old: \geq 85 ms 24 months/2 years to <6 years old: \geq 95 ms 6 to <12 years old : \geq 100 ms 12 to 16/18 years old : \geq 110 ms
At least grade 1 (adults)	>110 ms	
At least grade 2 (adults)	>120 ms	
High and increase from baseline (adults)		
At least grade 1	>110 ms and increase from baseline \geq 25%	
At least grade 2	>120 ms and increase from baseline \geq 25%	
QTc Fridericia		
Increase from baseline, Grade 1	Increase from baseline]30-60] ms	All age classes: Increase from baseline (30-60] ms

ECG Parameter	Adults	Children
PCSA criteria n/N1 (%)		
Increase from baseline, Grade 2	Increase from baseline >60 ms	All age classes: Increase from baseline >60 ms

References:

- for adults: Criteria for Potentially Significant Abnormalities – for Phase 2/3 studies (oncology excepted) - Version 3.0 - 21-MAY-2014
- for children: Criteria for Potentially Clinically Significant Abnormalities for Studies in Children - Version 3.0 - 21-MAY-2014

Vital signs parameter	Adults	Children
PCSA criteria n/N1 (%)		
Systolic blood pressure supine		
Low and decrease from baseline	≤ 95 mmHg and decrease from baseline ≥ 20 mmHg	Birth/0 to 27 days old : ≤ 60 mmHg and decrease from baseline ≥ 20 mmHg 28 days/1 month to 23 months old: ≤ 70 mmHg and decrease from baseline ≥ 20 mmHg 24 months/2 years to <6 years old: ≤ 70 mmHg and decrease from baseline ≥ 20 mmHg 6 to <12 years old : ≤ 80 mmHg and decrease from baseline ≥ 20 mmHg 12 to 16/18 years old : ≤ 90 mmHg and decrease from baseline ≥ 20 mmHg
High and increase from baseline	≥ 160 mmHg and increase from baseline ≥ 20 mmHg	Birth/0 to 27 days old : ≥ 85 mmHg and increase from baseline ≥ 20 mmHg 28 days/1 month to 23 months old: ≥ 98 mmHg and increase from baseline ≥ 20 mmHg 24 months/2 years to <6 years old: ≥ 101 mmHg and increase from baseline ≥ 20 mmHg 6 to <12 years old : ≥ 108 mmHg and increase from baseline ≥ 20 mmHg 12 to 16/18 years old : ≥ 119 mmHg and increase from baseline ≥ 20 mmHg
Diastolic blood pressure supine		
Low and decrease from baseline	≤ 45 mmHg and decrease from baseline ≥ 10 mmHg	Birth/0 to <6 years old : ≤ 34 mmHg and decrease from baseline ≥ 10 mmHg 6 to <12 years old : ≤ 48 mmHg and decrease from baseline ≥ 10 mmHg 12 to 16/18 years old : ≤ 54 mmHg and decrease from baseline ≥ 10 mmHg

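### The SAP plans no by-arm count of patients crossing an absolute QTcF level, and it replaces the protocol's by-arm ECG morphology summary with a listing without declaring the change

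*SAP*

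**What the plan says.** **Continuous summary.** SAP 2.4.5.5 gives summary statistics "of all ECG variables (central laboratory values and changes from baseline) will be calculated for each visit or study assessment", "based on the average of the triplicate assessments by treatment group". Minimum and maximum are included, and the worst on-treatment value is one of the assessments summarized.

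**Categorical summary.** The same section states: "The incidence of PCSAs at any time during the on-treatment period will be summarized by treatment group". The criteria are in SAP Appendix B. For QTcF there are two rows, the same for adults and children: "Increase from baseline]30-60] ms" (Grade 1) and "Increase from baseline >60 ms" (Grade 2). Neither has an absolute level. Heart rate, PR and QRS each have at least one row with a level.

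**Listings.** Patients above 480 ms or with "change from baseline in QTc/QTcB/QTcF >60 ms will also be listed separately". Morphology is covered by "A listing of morphological abnormalities (ECG extracted from 12-lead ECG data" and by a listing of patients with an abnormal qualitative assessment.

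**Protocol.** Table 9 (section 10.3.2) plans "A summary of ECG morphological assessments (for all high level types of comments by treatment arm". Section 3.3 names QTcF prolongation as an identified risk of both drugs. Section 9.2 makes QTcF of 500 ms or more, or a rise above 60 ms, a single adverse event of special interest (AESI). Exclusion criterion E 18 caps QTcF at 450 ms.

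**Declared changes.** SAP 1.6 does not mention the morphology output.

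**The concern.** QT prolongation is judged on two scales: how far a patient rises and how high the patient ends. The documents use both. They cap entry at a level, list patients above a level, and define an AESI partly by a level. The only by-arm categorical table built from the measured QTcF values uses the rise alone.

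Safety across OZ439 doses is a secondary objective, with about 35 patients per arm and descriptive analysis only. In that setting the useful display is n/N by arm at each cut-off. Without it, a reader must rebuild the counts from a listing that accepts QTc, QTcB or QTcF, so the count of QTcF cases has to be separated by hand.

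The morphology change is of another kind: an output planned by arm in the protocol is dropped from the by-arm tables, and the SAP does not say so. ST deviation, T-wave morphology and U-wave presence all come from the central reading (Protocol 9.4.3, SAP 2.1.5.5), so the data will exist.

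**Working it through.** The plan states no figure on this point, so there is none to reproduce. The check compares texts and adds threshold arithmetic.

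**Inputs.** Entry cap 450 ms (Protocol E 18). PCSA grades: rise above 30 to 60 ms, and above 60 ms (SAP Appendix B). Listing level above 480 ms (SAP 2.4.5.5). AESI level 500 ms or more (Protocol 9.2). About 35 patients per arm (SAP 1.1).

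**Step 1: rise needed from a baseline of at most 450 ms.**
- Above 480 ms: rise > 480 − 450 = 30 ms, so at least Grade 1.
- At or above 500 ms: rise ≥ 500 − 450 = 50 ms, so at least Grade 1.

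With the baseline capped at 450 ms, no patient above 480 ms escapes the PCSA count.

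**Step 2: what the grade hides.** A patient stays in Grade 1 with a rise of up to 60 ms.
- Above 480 ms within Grade 1: baseline > 480 − 60 = 420 ms.
- At or above 500 ms within Grade 1: baseline ≥ 500 − 60 = 440 ms.

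Baselines of 440 to 450 ms can therefore reach the AESI level and still be counted as Grade 1.

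**Step 3: what no grade captures.** A final value above 450 and up to 480 ms with a rise of 30 ms or less is in no by-arm QTcF category. It arises from baselines above 420 ms (450 − 30).

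**Step 4: which baseline applies.** Under Protocol 9.4.3, E 18 is judged on the automatic screening reading. Under SAP 2.1.5.5, the analysis baseline is the mean of the centrally read Day 0 triplicate. The two can differ, so a central baseline above 450 ms is possible. Such a patient could pass 480 ms with a rise of 30 ms or less.

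| Baseline → on-treatment QTcF (ms) | Rise | PCSA grade | Listed as >480 or rise >60 | AESI level |
|---|---|---|---|---|
| 380 → 435 | 55 | 1 | no | no |
| 450 → 505 | 55 | 1 | yes | yes |
| 448 → 478 | 30 | none | no | no |
| 452 → 481 | 29 | none | yes | no |

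**Step 5: size.** One patient is 1/35 = 2.9 percentage points of an arm. The documents give no outlier rate, so I assume 2%, 5% and 10%. The chance of at least one case in 35 is 1 − (1 − p)^35 = 51%, 83% and 97%. An arm with 0 of 35 has a two-sided 95% upper bound of 1 − 0.025^(1/35) = 10.0%.

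**Step 6: do other outputs supply the count?**
- The AESI table pools 500 ms or more with rises above 60 ms. SAP Table 2 identifies these cases through adverse event forms and a standardized MedDRA query, and reports them by preferred term.
- The continuous summary gives a maximum and a distribution per arm, not the number of patients beyond a level.
- The concentration-ECG models (SAP 2.4.6.3) predict mean change and omit the 72, 96 and 168 hour recordings.
- SAP 2.4.5.5 offers a split of PCSA counts by baseline status. A change-only criterion cannot classify a baseline value, so this split does not bring in the level either.

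**The case against.** A reader might infer that absolute QTcF appears only in listings, or that QT risk is not compared across OZ439 doses. The documents support neither reading. SAP 2.4.5.5 tabulates absolute central values by arm at each time point and for the worst on-treatment value. By-arm PCSA counts, AESI counts, a Torsade/QT query table and concentration-ECG predictions with 90% intervals, including QTcF at the highest dose combination, also show the risk by arm or dose.

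Nor does any passage promise by-arm absolute QTcF categories. Protocol 10.3.2.4 leaves PCSA thresholds to the sponsor, and Appendix B applies the sponsor's standard lists. With a baseline within the entry cap, every patient above 480 ms is both graded and listed. The only values outside every grade are then the mildest ones. On morphology, Protocol 10.3 calls itself a summary and defers to the SAP. The two listings keep every finding, and counts could be made from them for about 140 patients.

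Most of this stands and sets the limits of the point: adding absolute QTcF rows improves the plan and does not correct a departure from the protocol. Two things remain. No planned table gives the number of patients per arm beyond an absolute QTcF level. The morphology change is a departure from a by-arm output named in Table 9, and SAP 1.6 is where it should have been declared.

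**Conclusion.** The point holds as a reporting gap with two parts. First, there is no separate by-arm count of absolute QTcF outliers: patients above 480 ms are merged by size of rise, and values above 450 and up to 480 ms with a rise of 30 ms or less enter no by-arm QTcF category. Second, the protocol's by-arm morphology summary has become a listing without being declared.

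The size is modest. No sample size, power or primary result is affected, and no data are lost. At 2.9 percentage points per patient, a handful of cases would shape how the arms compare, and the planned counts cannot tell a high final QTcF from an equal rise at a low one.

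The claim that every patient above 480 ms is graded assumes a central baseline of at most 450 ms. Where the central Day 0 mean exceeds that, a patient could pass 480 ms outside any grade. The documents do not allow an estimate of how often this would happen.

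**What to change.** In SAP 2.4.5.5 and Appendix B:

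1. Add by-arm n/N (%) of treatment-emergent absolute QTcF, on the central triplicate mean, at cut-offs the documents already use: above 450, above 480, and at or above 500 ms. Place the rows next to the two change categories. Define treatment-emergent as beyond the cut-off on treatment and not at baseline, and state the denominator. These are reporting categories only.
2. Restore the Protocol Table 9 by-arm summary of morphology findings (ST deviation, T-wave, U-wave). If the sponsor prefers listings only, declare and justify that in SAP 1.6.
3. Keep the existing listings, with QTcF identifiable separately from QTcB.

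The cost is two descriptive tables from data already collected, plus SAP wording. No clinical rule, sample size or primary analysis changes.
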